4.4.2. Discontinuation of Investigational Product

Subjects must discontinue investigational product for any of the following reasons:

- Sponsor request, for reasons such as significant protocol deviation (and after discussion with the investigator).
- Study is terminated by the Sponsor.
- Subject meets PML discontinuation criteria (see [Appendix 4](#)).
- Subject develops any other serious opportunistic or atypical infection.
- Subject meets liver chemistry stopping criteria (see [Appendix 3](#)).
- Subject initiates treatment with a prohibited PV disease-modifying drug.
- Subject becomes pregnant.
- Subject experiences a serious or life-threatening cardiac arrhythmia.

Any subject who discontinues from the Treatment Period should complete an Early Withdrawal Visit and transition into the Individualized Follow-up Period for important safety monitoring (as applicable; see Section 3.1.3), unless he/she meets a criterion for mandatory withdrawal from the study (see Section 4.4.3).

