3.1.3. Follow-up Period

Subjects will be followed-up for a minimum of 4 weeks after the last dose of investigational product at the Week 56 visit. The follow-up visit will include B-cell counts and other safety, efficacy, and quality of life assessments.

If B-cell counts have not recovered by the Week 60 visit, subjects not entering the extension study (OPV117059) will remain in Individualized Follow-up until:

- CD19+ B-cell counts and circulating IgG levels are \geq LLN or baseline levels (if $<$ LLN)
- Other criteria for study withdrawal/exit are met (see Section 4.4.3)
- Two years after the last dose of investigational product (whichever comes first).

The Individualized Follow-up assessments should be scheduled approximately every 12 weeks. Subjects who withdraw from treatment will also enter the Individualized Follow-up Period.

Note: Subjects who are hepatitis B surface antigen (HBsAg) negative, hepatitis B core antibody (anti-HBc) positive, and hepatitis B virus (HBV) DNA negative (or if in Japan and HBsAg negative, anti-HBc (HBcAb) negative, but hepatitis B surface antibody [HBsAb] positive) must continue HBV DNA polymerase chain reaction (PCR) monitoring at a minimum of every 12 weeks for 6 months after the last dose of study treatment.

For subjects who participate in the extension study, OPV116910 (also known as COMB157J2301) Week 60 study assessments will be completed before any study-related assessments are performed for the extension study.

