- e. Premedication: Each dose of study treatment will be preceded by acetaminophen/paracetamol and an antihistamine (see Section 5.1.2).
Postdose observation and medication: After the first dose, subjects should stay at the clinic to be monitored for any injection-related AEs for a minimum of 4 hours, with acetaminophen/paracetamol administered again at 4 hours. After subsequent doses, it is recommended that subjects stay at the clinic for a minimum of 1 hour, with acetaminophen/paracetamol self-administered approximately 4 to 6 hours after dosing if needed.
Note: An additional 20-mg loading dose (total of two 20-mg injections) will be administered at Week 0 and Week 4.
- f. Laboratory assessments include hematology, clinical chemistry, and urinalysis. "H" indicates visits with only hematology.
At Screening and Week 60/early withdrawal only—Hepatitis B, Hepatitis C, pneumococcal antibody assay, and toxoid antibody assay.
- g. Collect sample predose on dosing days.
- h. Informed consent must be obtained before collecting samples for optional testing (ie, pharmacogenetics research and pharmacokinetic-pharmacodynamic substudy analyses).
- i. Only sites preidentified to participate in pharmacokinetic-pharmacodynamic substudy. See Table 6-3 for the schedule of visits for sample collection.

Note: Visits from Week 2 through Week 60 to be scheduled within ±3 days of the specified time point. Visits during Individualized Follow-up to be scheduled within ±7 days.

Table 6-2 Time and Events Table: Individualized Follow-up Period

	As applicable ^a								Early WD
Study Week for Core Study Completers:	72	84	96	108	120	132	144	156	
Study Week for Early Withdrawals:	+12	+24	+36	+48	+60	+72	+84	+96	
Adverse events (including SAEs and AEs of special interest) ^b	X	X	X	X	X	X	X	X	X
Concomitant medications	X	X	X	X	X	X	X	X	X
Document steroid dose	X	X	X	X	X	X	X	X	X
Neurological symptoms questionnaire (PML monitoring)	X	X	X	X	X	X	X	X	X
PV lesion mapping	X	X	X	X	X	X	X	X	X
Pregnancy testing (urine) (women) – test monthly for 12 months after the last dose of ofatumumab SC; subjects may test at home during months without a clinic visit	X	X	X	X					X
Hematology	X	X	X	X	X	X	X	X	X
Clinical chemistry	X	X	X	X	X	X	X	X	X
IgG, IgM, IgA	X	X	X	X	X	X	X	X	X
Human anti-human antibody	X								X
Pharmacodynamic markers (flow cytometry)	X	X	X	X	X	X	X	X	X
HBV DNA – if applicable, test every 12 weeks for 6 months after the last dose of ofatumumab SC	PRN	PRN							PRN

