8.2. Study Design Considerations

8.2.1. Sample Size Assumptions

Assuming that the proportion of subjects achieving SR on minimal steroid therapy status is 54% and 80% in the placebo and the ofatumumab SC groups, respectively [Beissert, 2010], with proportional hazards across the various strata, a sample size of 68 subjects per group will give $\geq 90\%$ power for a statistically significant difference between the two groups in time to SR on minimal steroid therapy, using a two-sided 0.05 level of significance. Note that for the purpose of sample size calculation of time to SR, “survival” means: “Not in SR”, and hence $(100-54=)$ 46%, and $(100-80=)$ 20% are the survival rates for the placebo and ofatumumab SC treatment groups respectively needed to calculate sample size for the log-rank test. The study is designed to detect a hazard ratio of 0.48248 (median time to response on ofatumumab SC/median time to response on placebo). It is assumed that no more than 13% of the subjects in both groups will be lost to follow-up before their Week 60 visit. With the projected 54% and 80% SR rates in the placebo and active groups respectively, a total of approximately 80 subjects with SR in both treatment groups combined are needed at the end of the study. Because this study has 2 co-primary efficacy endpoints, an evaluation of the overall power to detect at least one significant endpoint was made using simulations. The analysis proposed for the

co-primary endpoints is a sequential test based on the method of Alosch and Huque [Alosch, 2010]. Results of the simulations are displayed in Table 8-2.

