9.1.2.2. Remission

For the secondary endpoint of the proportion of subjects in remission on minimal steroid therapy at Week 60, subjects who discontinued treatment prior to Week 60 will be considered as not in remission at Week 60.

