11.1. Primary Efficacy Analyses

11.1.1. Time to SR on Minimal Steroid Therapy by Week 60

The co-primary efficacy endpoint of time to SR on minimal steroid therapy by Week 60 (as defined in Section [2.2.1](#)) will be analyzed using a log-rank test stratified by baseline prednisone/prednisolone dose and disease duration strata. Subjects who discontinue prematurely (prior to Week 60) and who have not achieved remission upon discontinuation will be censored at the time they discontinued. Subjects who reach Week 60 without remission will be censored at the date of their last visit.

For subjects achieving remission, time to SR on minimal steroid therapy will be derived as: [(the date on which the subject initially tapered his/her oral prednisone/prednisolone dose to ≤ 10 mg/day and maintained ≤ 10 mg/day of oral prednisone/prednisolone with no new or nonhealing (established) lesions for ≥ 8 weeks and maintained that status until Week 60) – (the date of randomization)] + 1 day.

A summary table presenting the Kaplan-Meier estimates for the time to SR and 95% CI at Week 4, week 8, Week 12 etc. for each of the treatment groups and p-value for the treatment difference, using the 2-sided log-rank test indicated above will be presented for the ITT population and PP population (if criteria are met as discussed in Section [11](#)).

For the covariate analysis, a summary table computing hazard ratio and 95% CI for the hazard ratio and the p-value using the Cox proportional hazards model discussed in Section [8.2](#), will be presented for the full model for the ITT population.

A Kaplan-Meier plot of time to SR on minimal steroid therapy will be constructed for each treatment group for the ITT population.

11.1.2. Duration of Remission on Minimal Steroid Therapy by Week 60

The co-primary endpoint of duration of remission on minimal steroid therapy will be analyzed using a rank ANCOVA [[Stokes 2000](#)], with treatment as a main effect, and baseline prednisone/prednisolone dose and disease duration strata as covariates. If a subject discontinues the study prior to Week 60, the subject will be considered as not in remission from the date of the last known study visit until Week 60.

For subjects who complete the study without experiencing any periods of remission, duration of remission on minimal steroid therapy will be 0 days.

One Period of Remission

For subjects who experience one period of remission on minimal steroid therapy that:

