- Is continuing at the Week 60 study visit (or early discontinuation):

- Duration of remission on minimal steroid therapy will be derived as: [(the date of the Week 60 study visit/date of last known visit) - (the date on which an absence of new or nonhealing lesions occurs while the subject is on a prednisone/prednisolone dose of ≤ 10 mg/day for ≥ 8 weeks)] + 1 day.
- Relapses/flare prior to the Week 60 study visit (or early discontinuation):
 - Duration of remission on minimal steroid therapy will be derived as: [(the date on which flare/relapse occurs) - (the date on which an absence of new or nonhealing lesions is found while the subject is on a prednisone/prednisolone dose of ≤ 10 mg/day for ≥ 8 weeks)].

Note that for periods of remission that end with relapse/flare, “+ 1 day” is not included in the calculation since the end date is the date on which relapse/flare occurs so the subject is not considered to be in remission on that day.

More Than One Period of Remission

For subjects who experience more than one period of remission on minimal steroid therapy (i.e. a subject went into remission, then relapsed, and then went into remission again (or possibly more than 2 episodes of remission)) the duration of remission will be the sum of all periods of remission while on minimal steroid therapy up to Week 60.

Individual periods of remission will be defined as specified above for subjects experiencing one period of remission. Duration of remission will be derived as the sum of all individual periods of remission.

A summary table computing the raw duration and p-value for the treatment difference, using the rank ANCOVA indicated above, will be presented for the ITT population and PP population (if criteria are met as discussed in Section [11](#)).

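### Duration of remission runs to an undefined last visit; if off-treatment follow-up visits count, follow-up driven by B-cell and IgG recovery can lengthen this co-primary by arm

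*Protocol*

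**What the plan says.** **Follow-up after stopping product.** Protocol 4.4.2: "Any subject who discontinues from the Treatment Period should complete an Early Withdrawal Visit and transition into the Individualized Follow-up Period". Protocol 3.1.3 adds: "The Individualized Follow-up assessments should be scheduled approximately every 12 weeks". Table 6-2 (Protocol Section 6) counts these visits from withdrawal. Its row "Study Week for Early Withdrawals" runs from +12 to +96 weeks in steps of 12, with lesion mapping and steroid dose at each visit and none tied to Week 60. No section keeps a discontinuer on the Table 6-1 efficacy schedule.

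**How long it lasts.** Protocol 3.1.3 and Table 6-2 footnote a end Individualized Follow-up (IFU) when both CD19+ count and IgG have recovered, with a two-year maximum. Protocol 3.3 predicts 99% median B-cell inhibition on ofatumumab and a median of about 28 weeks to repletion after dosing stops.

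**The duration rule.** Under SAP 11.1.2, if a subject discontinues the study before Week 60, "the subject will be considered as not in remission from the date of the last known study visit until Week 60". An ongoing remission ends at "the date of the Week 60 study visit/date of last known visit". Protocol 8.3.2, 8.3.6.1 and 8.3.6.5 carry the same rule. For the Week 60 proportion, SAP 9.1.2.2 uses a different trigger: "subjects who discontinued treatment prior to Week 60 will be considered as not in remission at Week 60".

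**The concern.** The protocol separates stopping product (4.4.2) from leaving the study (4.4.3). A subject in IFU has done only the first. Read literally, such a subject has not discontinued the study, and an IFU visit before Week 60 can be the last known visit. The length of IFU depends on markers that ofatumumab alters and placebo does not. One literal application of a co-primary rule therefore makes the observable window depend on treatment.

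Two subjects with the same course, both stopping at Week 24 in remission on 10 mg/day or less, could receive different durations because one is still B-cell depleted. Two programmers could also derive different values from the same data. What is at stake is the level of the rank ANCOVA on duration. The SAP reports that test at a nominal two-sided 5% without multiplicity adjustment (8.3, 11.1.3).

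**Working it through.** **1. The plan's own figure.** The documents give no figure for this asymmetry. Their sample size reproduces: Protocol 8.2.1 says "a sample size of 68 subjects per group will give" at least 90% power "using a two-sided 0.05 level of significance".
- Hazard ratio = ln(0.46)/ln(0.20) = 0.48248.
- Events (Schoenfeld) = 4(1.960 + 1.282)²/(ln 0.48248)² = 79.1, rounded up to 80; power with 80 events is 90.3%.
- N = 79.1/0.67/0.87 = 135.7, i.e. 136, where 0.67 is the mean of 0.54 and 0.80.

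This rests on time to sustained remission, so the present point does not change it.

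**2. Is IFU anchored to Week 60?** For withdrawal at dosing visit w = 4, 8, ..., 56, an IFU visit falls on Week 60 only if (60 − w)/12 is a whole number: w = 12, 24, 36 or 48, so 4 of 14.

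**3. Extra observable time per depleted discontinuer, if IFU visits count.** Release is at the first 12-weekly visit at or after repletion. Extra time is the last such visit not later than Week 60, minus w.

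| Stop at week | Repletion at 24 wk | Repletion at 28 wk |
|---|---|---|
| 8, 16, 24 | 24 | 36 |
| 32 | 24 | 24 |
| 40, 48 | 12 | 12 |

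A placebo subject with normal markers gets 0 weeks if discharged at Early Withdrawal, or about 12 if entered and released at the first IFU visit.

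This is observable time, not remission time. From 20 mg/day the taper gives 17.5, 15, 12.5 and 10 mg at Weeks 2, 4, 6 and 8, so eight weeks at 10 mg are complete no earlier than Week 16. From 50 mg, 10 mg is reached at Week 16 and eight weeks are complete at Week 24; from 60 mg, at Weeks 18 and 26. A Week 24 discontinuer already in remission therefore started at 50 mg or less.

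**4. Effect on the test, simulated under the null.** Remission and flare processes were identical in both arms, with a rank test on total duration without covariates and 2,000 trials per cell. Assumptions not in the documents:
- discontinuation uniform over 60 weeks;
- exponential time to remission, mean 28 weeks (Table 8-2, first row, read as a mean);
- exponential time to flare, mean 40 or 200 weeks;
- log-normal repletion, median 28 weeks and log-SD 0.35;
- last dose 0 to 4 weeks before withdrawal;
- no taper floor, and every ofatumumab discontinuer attends IFU.

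One-sided type I error (nominal 0.025), ranges over the two flare means:

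| Per arm, share stopping | IFU counts; placebo ends at Early Withdrawal | IFU counts; placebo has one +12-week visit |
|---|---|---|
| 68, 13% | 0.061–0.064 | 0.040–0.043 |
| 68, 30% | 0.150–0.160 | 0.069–0.086 |
| 34, 60% | 0.29–0.34 | 0.11–0.13 |

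With both arms cut at Early Withdrawal, the error was 0.023–0.028 across the scenarios run. Monte Carlo error is about 0.004 near 0.025 and about 0.01 for the larger values.

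In the first cell the mean duration differs by 23.85 − 22.67 = 1.2 weeks (flare mean 40) or 31.52 − 29.88 = 1.6 weeks (flare mean 200). The planning gaps in Table 8-2 are 17 − 8 = 9, 17 − 9 = 8 and 19 − 10 = 9 weeks.

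**The case against.** **The intended cut-off may already be the Early Withdrawal visit.** Protocol 4.4.2 goes on to describe IFU as safety monitoring, and Protocol 8.3.5 puts IFU data in a report addendum. The sub-headings in SAP 11.1.2 pair the Week 60 visit with early discontinuation, and SAP 10.1 ends the core period the same way. On that reading there is no differential. This stands as a plausible reading, but it is not stated as a rule. The SAP provides for one final analysis on the available data (4.1, 4.2). It limits IFU safety data to listings (Section 12) without a matching limit for efficacy. For the secondary endpoints it takes lesion status from all post-baseline clinic visits (11.2.1). Its slotting rule (9.3.3) sends IFU records to visit windows by study day, yet Table 9-1 has no IFU rows.

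**A reader might infer that placebo discontinuers cannot earn post-withdrawal time.** The documents do not support that. The protocol definitions, the Protocol Summary and 3.1.3 send all treatment withdrawals to IFU; 3.1 and 4.4.2 add a qualifier, and Table 6-1 footnote b makes entry depend on depletion. A placebo subject with low IgG, or under hepatitis B monitoring, may also stay. The SAP (Section 3 and 3.4) ends IFU when either marker recovers, against both in the protocol, which would shorten it for depleted subjects with normal IgG.

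**A reader might infer that censoring of time to sustained remission is biased the same way.** It need not be. SAP 11.1.1 censors at discontinuation. If IFU did extend follow-up of event-free ofatumumab subjects, the added time at risk would work against ofatumumab, in line with the reasoning in Protocol 8.3.6.1.

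**A reader might apply the protocol's 13% to count affected subjects.** That rate is for loss to follow-up. Such subjects do not attend IFU, and those who withdraw consent leave the study (4.4.3). The 13% in the simulation is likewise only an assumed stopping rate.

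**Conclusion.** Two things are certain. Off-treatment lesion and steroid follow-up depends on markers that treatment changes, and the last known visit is undefined for a co-primary endpoint. The bias itself is conditional. If IFU visits before Week 60 count, duration of remission favours ofatumumab; if they do not, there is no differential. A reader might take the bias as established, but the passages for a core-only reading prevent that.

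If the visits count, the one-sided error at 68 per arm and 13% stopping is about 0.04 to 0.06 instead of 0.025, with a mean shift of 1.2 to 1.6 weeks, on assumed inputs and with full IFU attendance. The larger figures need a high stopping rate. That is relevant because sponsor termination is a listed reason to stop product and the trial ended early with 69 randomized (SAP Section 5), but the documents do not say how many stopped for that reason. The point should be corrected before analysis, because the remedy is almost free.

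**What to change.** In SAP 9.1.2.1 and 11.1.2, define the last known visit and the censoring date for both co-primaries as the last Core Study visit, including Early Withdrawal, in both arms. Exclude IFU lesion and steroid records from both co-primaries, and use the discontinuation trigger of SAP 9.1.2.2. This takes about one sentence and needs no new data. The downside is that some observed post-withdrawal remission time is not used.

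Also reconcile two sets of passages:
- **IFU entry:** the protocol definitions, Protocol Summary and 3.1.3 against 3.1, 4.4.2 and Table 6-1 footnote b.
- **IFU exit:** Protocol 3.1.3 and Table 6-2 footnote a against SAP Section 3 and 3.4.

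Keeping discontinuers on lesion and steroid assessments to Week 60 whatever their B-cell status would be the stronger design, at the cost of extra visits. It is an option for a future trial, since this one has been terminated.

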4.4.3. Withdrawal from the Study

Subjects must discontinue investigational product and be withdrawn from the study for the following reasons:

- Subject withdraws consent.
- Subject initiates treatment with a prohibited PV disease-modifying drug that depletes B-cells (eg, rituximab).
- Sponsor request (after discussion with the investigator).

** In **Japan**, refer to [Appendix 2](#) for applicable country-specific details. **

5. STUDY TREATMENTS

5.1. Investigational Product and Other Study Treatment

5.1.1. Investigational Product

Ofatumumab SC (GSK1841157; human mAb ofatumumab injection for SC use) will be supplied by Novartis as a liquid concentrate in a prefilled glass syringe with staked needle, stopper, and plunger, with a needle safety device. Initially, syringes containing 0.6 mL (60 mg) of concentration 100 mg/mL drug product will be provided.

Placebo in prefilled glass syringes to match the ofatumumab syringes, will be made and supplied by Novartis, using normal saline (sterile, pyrogen-free 0.9% NaCl) and filled to

0.6 mL in a prefilled glass syringe with staked needle, stopper, and plunger, with a needle safety device.

Contents of the label will be in accordance with all applicable regulatory requirements.

For study centers initiated using the dilution method for study treatment preparation, an unblinded pharmacist (or appropriately-qualified designee) at the study center will prepare each dose via a dilution process according to the detailed instructions in the pharmacy manual. Briefly, the contents of 2 prefilled (0.6 mL) syringes (either 1 ofatumumab 60-mg syringe plus 1 placebo syringe or 2 placebo syringes) will be injected into a sterile vial and 0.4 mL of the resulting solution will be drawn into a new syringe to achieve the 20-mg ofatumumab (concentration 50 mg/mL) or placebo dose. Solutions obtained from the dilution method will be filtered through Kendall 5 micron filter needles prior to injection. The in-use time after the drug product is drawn into the syringe for administration should not exceed 2 hours; however, it is recommended that the drug product be administered immediately.

In countries (including Japan) and/or study centers not using the dilution method to prepare study injections, Kendall 5 micron filter needles will not be used and there is no need to designate an unblinded pharmacist (or appropriately-qualified designee) for drug preparation.

When available, Novartis will supply ofatumumab SC in prefilled glass syringes containing 0.4 mL (20 mg) of concentration 50 mg/mL drug product and matching placebo prefilled glass syringes containing 0.4 mL of normal saline.

Trained site personnel will administer 0.4 mL of investigational product via SC injection into a vertical fold of abdominal skin approximately 2 to 4 inches lateral of the umbilicus. The injection site may be adjusted at investigator's discretion if there are extensive abdominal lesions present. Subjects should stay at the clinic for a minimum of 4 hours after the first dose of investigational product to be monitored for any injection-related AEs. It is recommended that subjects stay at the clinic for a minimum of 1 hour, at the investigator's discretion, after each subsequent dose.

Sites should adhere to dosing on the specific visit schedule as shown in [Table 6-1](#).

Protect investigational products from light and store in a refrigerator at 2° to 8°C (36° to 46°F); do not freeze. Store the investigational product in a secure area under appropriate physical conditions. Access to and administration of the investigational product is limited to the investigator and authorized site staff. Dispense or administer investigational product only to subjects enrolled in the study and in accordance with the protocol. The study monitor will be responsible for reviewing drug accountability of the investigational product at the site. Detailed instructions related to the destruction of unused materials are provided in the pharmacy manual.

Under normal conditions of handling and administration, investigational product is not expected to pose significant safety risks to site staff. A Material Safety Data Sheet describing the occupational hazards and recommended handling precautions will be provided to site staff in the pharmacy manual.

